4.13 Safety Analyses

All safety evaluations will be based upon the Safety Analysis Set.

Safety will be assessed by evaluating all reported AEs and changes in laboratory analytes, ECGs, and vital signs (including body weight) in the Safety Analysis Set and summarized by treatment group.

The baseline for computing the change in safety data is the last value collected before the first dose of study drug. The parameters will be listed and summarized with standard descriptive statistics. Change from baseline will also be summarized.

4.13.1 Extent of Exposure

Exposure to therapy will be calculated for each subject as the number of complete infusions delivered.

4.13.2 Adverse Events

Summaries of AEs will include the number of patients with at least one AE for each treatment group. When reporting by system organ class (SOC) and preferred term (PT), the reports will present the SOC in alphabetical order; while PTs within the SOC will be presented in order of overall decreasing frequency of occurrence overall. A patient with multiple AEs (different PTs) coded to the same SOC will be counted only once for that SOC, but will be counted each time for different PTs within that SOC. A patient with separate events of the same PT (different start/stop dates) will be counted only once in the frequency tables for that PT.

A treatment-emergent adverse event (TEAE) is defined as an event that first occurred or worsened in severity after baseline. The MedDRA Lowest Level Term (LLT) will be used in the treatment-emergent computation. The maximum severity for each LLT during the screening period will be used as baseline. The treatment period will be included as post-baseline for the analysis.

AEs will be coded according to the Medical Dictionary for Regulatory Activities and summarized by system organ class, preferred term, severity, and relationship to investigational product. For each event classification term, the number of subjects experiencing a TEAE with that classification term will be tabulated.

In an overview table, the number and percentage of patients who experienced a TEAE, serious adverse event, adverse event related to study drug, died due to an adverse event, or discontinued from the study due to an adverse event will be summarized by treatment. TEAEs will be reported separately for Days 1-28 while in the hospital and for the post-hospitalization follow-up period.

Treatment-Emergent Adverse Events

Treatment-emergent adverse events (TEAE) include all adverse events that emerge or worsen after taking the first dose of study drug. TEAEs will be summarized for each treatment group by SOC and PT, and by PT in order of decreasing frequency of preferred term.

Serious Adverse Events

Treatment-Emergent SAEs will be summarized for each treatment arm by SOC and PT. These reports will also include the total number of SAE for each SOC and PT.

Treatment-Emergent Adverse Events Resulting in Death

If there are any TEAEs that result in death, a listing of all deaths will be provided. In addition, a summary table may also be created by PT in order of decreasing frequency of preferred term.

Treatment-Emergent Adverse Events Leading to Study Drug Discontinuation

TEAEs for which the action taken with medication is ‘Drug Withdrawal’ will be identified as TEAEs that lead to study drug discontinuation. The TEAEs that lead to study drug discontinuation will be summarized for each treatment group by SOC and PT for the Safety population.

Treatment-Related Treatment-Emergent Adverse Events

Every AE will be assessed by the investigator for its relationship to the randomly assigned study medication. The subset of TEAEs considered by the investigator as either possibly, probably, or definitely related to study treatment will be summarized as drug-related TEAEs by SOC and PT.

Treatment-Emergent Adverse Events by Maximal Severity

Every AE will be graded by the CTCAE criteria, so for each patient the greatest severity observed can be obtained by comparing the severity of all of a patient’s TEAEs that share the same SOC or PT. A table of TEAEs by maximal severity will be prepared for each treatment arm by SOC and PT.

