Randomization will be stratified by age group (<65 years and \geq 65 years), sex and site.

Secondary efficacy analyses will assess secondary endpoints as well as analyses of relevant subgroups.

Safety analyses will include assessments of adverse events, vital signs, electrocardiograms and laboratory parameters.

An independent Data Monitoring Committee will be used to monitor unblinded safety data.

2. Schedule of Activities

Table 2-1. Schedule of Activities

Study Day	S ^a	Treatment						Completion or Hospital Discharge or ED ^{b,c}	Follow-Up Phone Visit 1 ^d	Follow-Up Phone Visit 2 ^d
	≤1	1	2	7	15	16	21	28 (or the day discharged from hospital or ED)	42 ^d	60
Window Period (days)		-	-	±2	-	-	±2	±1	±2	±2
Eligibility review	X									
Informed consent	X									
Demographics	X									
Medical history ^e	X									
Height	X									
Weight	X							X		
Physical examination (directed unless otherwise noted)	X (complete)	X		X	X		X	X (complete)		
Vital signs ^f	X	← Every day from Day 1 to 27 → Predose and postdose on Days 1 and 15						X		
Hematology and clinical chemistry		X (pre-dose) ^g	X	X	X (pre-dose)	X	X	X		
COVID-19 panel ^h		X (pre-dose)	X	X		X	X	X		
Influenza/RSV/respiratory viral panel ⁱ		X								
Thyroid function test (TSH and FT4)		X (pre-dose)						X		
Pregnancy Test ^j	X (serum / urine)							X (urine)		
12-Lead ECG ^k		X (pre-and post-dose) ^l			X (pre-and post-dose)			X		

	S ^a	Treatment						Completion or Hospital Discharge or ED ^{b,c}	Follow-Up Phone Visit 1 ^d	Follow-Up Phone Visit 2 ^d
Study Day	≤1	1	2	7	15	16	21	28 (or the day discharged from hospital or ED)	42 ^d	60
Window Period (days)		-	-	±2	-	-	±2	±1	±2	±2
Randomization ^m		Within 24 hours of screening								
Study drug administration ⁿ		Within 8 hours of randomization			X					
SpO ₂ , O ₂ flow rate ^o	X	← Every day from Day 1 to 27 →						X		
NIAID ordinal assessment ^p	X	← Every day from Day 1 to 27 →						X	X	X
Adverse event monitoring ^q		← Every day from Day 1 to 27 →						X	X	X
Supportive pulmonary care ^r		← Every day from Day 1 to 27 →						X		
Concomitant medications ^s		← Every day from Day 1 to 27 →						X		

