Abbreviations: ECG = electrocardiogram; ECMO = extracorporeal membrane oxygenation; ED = early discontinuation; fT4 = free thyroxine; FU = follow-up; h = hours; ICF = informed consent form; IMV = intermittent mandatory ventilation; NIAID = National Institute of Allergy and Infectious Diseases; PK = pharmacokinetic; S = Screening; SO₂ = oxygen saturation; TSH = thyroid stimulating hormone.

- a Any procedure done as a standard of care 1 calendar day prior to ICF may be used as the screening procedure. Screening and Day 1 may occur on the same day.
- b Patients who are discharged from the hospital will complete the Completion or Hospital Discharge visit procedures
- c Patients who discontinue the study prior to study completion will complete the ED visit procedures.
- d Follow-up phone visit 1 should be conducted at 14 days after completion or hospital discharge or early discontinuation, or 28 days after the first dose of study drug, whichever occurs later. Follow-up phone visit 2 should be conducted at 60 days after first dose of study drug.
- e Ensure the onset of illness symptoms are captured, examples include fever, coughing, extreme fatigue, headache, myalgia.
- f Includes respiration rate, heart rate, temperature, and blood pressure. Vital signs need to be recorded once at approximately the same time each day. Post dose vital signs on Days 1 and 15 should be collected at the end of infusion and at approximately 1 hr after end of infusion.
- g If procedures were performed within 1 calendar day prior to infusion as part of standard of care and prior to ICF, that may be used as the sample collection on Day 1.
- h Data should be collected from local COVID19 panel laboratory pre-dose within 1 calendar day ≤Day 1, between 24 and 48 hr postdose on Day 2, and Day 16; and at any time on Days 7, 21, and 28 (or discharge or ED). Collection on Days 16 and 21 to be performed only if a Day 15 dose of study treatment was administered ([Appendix 2](#)).

- i Viral testing is only performed for patients who have undetermined or negative COVID-19 test(s). Viral testing is per the institution's testing guidelines.
- j For pregnancy test, only for women of child-bearing potential.
- k Single 12-lead ECGs will be obtained in the supine position at all indicated timepoints. On Days 1 and 15, ECGs will be collected pre-dose and at the end of infusion.

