3.3. Benefit/Risk Assessment

The potential benefit of LY3127804 has been described in Section 3.2. Based on the nonclinical safety data and clinical data reported so far, LY3127804 initial clinical data have shown it to have an acceptable safety profile at the dose selected for this study. Given the lack of any available therapy that has shown to be effective in preventing progressive pulmonary failure and

progression to ARDS in patients with viral induced pneumonia, there currently exists an acute need for such treatment to address the immense unmet medical need resulting from large numbers of patients presenting with COVID-19, some of which will progress to ARDS with unacceptably high mortality. Given the acceptable safety profile of LY3127804 and the dire prognosis for patients progressing to ARDS secondary to SARS-CoV-2 infection, the potential benefit of LY3127804 outweighs the potential risk.

More information about the known and expected benefits, risks, serious adverse events (SAEs) and reasonably anticipated adverse events (AEs) of LY3127804 are to be found in the Investigator's Brochure (IB).

4. Objectives and Endpoints

Objectives	Endpoints
Primary	

 To evaluate ventilator free days during treatment with LY3127804 	
 Number of days from Day 1 to Day 28 on which a patient breathes without assistance, if the period of unassisted breathing lasted at least 24 consecutive hours and the patient did not die within 28 days from first dose of study drug
Secondary	

 To evaluate clinical status of patients during treatment with LY3127804 	
 NIAID ordinal assessment (see Section 9.1.2.1 for definition)

 To evaluate survival without the need for IMV/ECMO in patients treated with LY3127804 	
 Proportion of patients who are alive and respiratory failure free (i.e. never having required mechanical ventilatory support) by Day 28

 To evaluate mortality rate during treatment with LY3127804 	
 Death within 28 days from first dose of study drug

 To evaluate reduction in hospital stay during treatment with LY3127804 	
 Length of hospitalization

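### The by-period TEAE report in SAP 4.13.2 has no place for inpatient events after Day 28 and compares unequal time at risk, although the unsplit tables should still hold those events

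*SAP*

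**What the plan says.** SAP 4.13.2 plans an overview table and summaries of treatment-emergent events by system organ class and preferred term for each arm. After the overview table it adds a split: "TEAEs will be reported separately for Days 1-28 while in the hospital and for the post-hospitalization follow-up period". No rule covers an event that meets neither description, and the table list in SAP 5.1 names no by-period table.

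Two sentences in the same section bear on how late an event can occur and still count. One sets no end date: "Treatment-emergent adverse events (TEAE) include all adverse events that emerge or worsen after taking the first dose of study drug". The other reads "The treatment period will be included as post-baseline for the analysis"; the end of that period is not defined.

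In Protocol Table 2-1 the completion column is headed "28 (or the day discharged from hospital or ED)", so a patient still in hospital has the completion visit at Day 28. The row "Adverse event monitoring" is marked daily to Day 27, at completion or discharge, and at both phone visits. Footnote d says "Follow-up phone visit 1 should be conducted at 14 days after completion or hospital discharge or early discontinuation", or 28 days after first dose if that is later, and "Follow-up phone visit 2 should be conducted at 60 days after first dose of study drug".

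Protocol Section 4 lists the secondary objective "To evaluate reduction in hospital stay during treatment with LY3127804", and SAP 4.12.3.4 compares Day 28 discharge rates between arms. Under SAP 4.13.1, exposure is a count of completed infusions. No person-time denominator is planned for adverse events.

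**The concern.** There are two separate problems.

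**Coverage.** The first period requires both a study day up to 28 and inpatient status. The second requires that the hospital stay has ended. A patient who remains in hospital after Day 28 meets neither condition from Day 29 until discharge, yet is still being followed for adverse events. These are long-stay patients. Secondary infections, the event of special interest in Protocol 9.2.4, are exempt from serious-event reporting under Protocol 9.2.1 unless judged drug-related. The adverse event tables are therefore a main place to see late inpatient infections.

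**Comparability.** Discharge happens after randomization and is itself an outcome of the trial. If one arm leaves hospital sooner, it has fewer days at risk in the first period, and a percentage of patients with an event will be lower there without any difference in daily risk. Longer stays would produce an apparent harm in the same way. Earlier death also shortens the first period, so an arm with more early deaths could look better in hospital.

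**Working it through.** The plan attaches no figure to this split, so there is none to reproduce.

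**Coverage, by reading.** Take a patient in hospital without interruption to Day 40, with an event on Day 35.
- Period 1 fails because Day 35 is after Day 28.
- Period 2 fails because the patient has not been discharged.
- The event is collected, because this patient completes at Day 28 and is phoned 14 days later, at Day 42.
- The event is treatment-emergent under the SAP definition that has no end date, so it enters the unsplit tables.

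**Comparability, by illustration.** The inputs are assumptions: a constant hazard λ, the same in both arms and in or out of hospital; exponential length of stay with mean m days; no deaths.

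P(at least one in-hospital event by Day 28) = λ/(λ + 1/m) × [1 − exp(−28(λ + 1/m))]

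For λ = 0.05:
- m = 12: 0.05/0.13333 × [1 − exp(−3.733)] = 0.375 × 0.976 = 36.6%.
- m = 9: 0.05/0.16111 × [1 − exp(−4.511)] = 0.310 × 0.989 = 30.7%.
- Gap: 5.9 points, with no true difference in risk.

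| λ per day | Mean stay 10 vs 8 | 12 vs 9 | 14 vs 10 |
|---|---|---|---|
| 0.02 | 16.1% vs 13.6% (2.5) | 18.3% vs 14.9% (3.4) | 20.2% vs 16.1% (4.1) |
| 0.05 | 32.8% vs 28.4% (4.5) | 36.6% vs 30.7% (5.9) | 39.8% vs 32.8% (7.0) |
| 0.10 | 49.8% vs 44.4% (5.5) | 54.2% vs 47.2% (7.0) | 57.8% vs 49.8% (8.0) |

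Gaps in points are in brackets. The range is 2.5 to 8.0. Wider stay contrasts give more: 12 vs 7 days at λ = 0.10 gives 54.2% vs 41.1%, about 13 points.

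**Time at risk.** Mean in-hospital days up to Day 28 are m[1 − exp(−28/m)]: 10.8 for m = 12 and 8.6 for m = 9. Mean days from discharge to Day 60 are 60 − m[1 − exp(−60/m)]: 48.1 and 51.0. The second period therefore tends the other way.

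**Size of the uncovered group.** P(still in hospital after Day 28) = exp(−28/m): 9.7% for m = 12 and 4.5% for m = 9. Across the stays in the table it is 6.1% to 13.5% in the longer-stay arm and 3.0% to 6.1% in the other. The chance of an unassigned event by Day 60 is smaller, since the patient must also have one in that time: exp(−28/m) × λ/(λ + 1/m) × [1 − exp(−32(λ + 1/m))]. At λ = 0.05 this is 0.097 × 0.375 × 0.986 = 3.6% for m = 12, and 0.0446 × 0.310 × 0.994 = 1.4% for m = 9.

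**Fixed Day 1-28 window.** With complete ascertainment, P = 1 − exp(−28λ) in both arms: 42.9%, 75.3% and 93.9% at λ = 0.02, 0.05 and 0.10. The expected difference is zero.

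**Incomplete phone recall.** Suppose phone contact captures a fraction c of post-discharge events. With a = 1/m + (1 − c)λ,

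P = 1 − {exp(−28cλ) × [1 − exp(−28a)]/(ma) + exp(−28/m) × exp(−28λ)}

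At λ = 0.05 and stays of 12 vs 9 days, the fixed-window gap is 3.6 points at c = 0.25, 2.0 at c = 0.50 (61.2% vs 59.3%) and 0.8 at c = 0.75, against 5.9 for the in-hospital split.

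**The case against.** The strongest reply is that the split is a secondary display. The TEAE and SAE summaries in SAP 4.13.2, Tables 8-14 in SAP 5.1 and Listings 8-10 in SAP 5.2 carry no period or hospital-status restriction. That stands. A reader might infer that late inpatient events are lost from the safety analysis; the documents do not support this.

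A reader might also infer that the SAP limits treatment-emergent events to the treatment period. It says that this period is included as post-baseline, not that nothing else is, and the companion definition has no end date. The wording is loose and needs an explicit end point, but it is not a stated exclusion.

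The split also has a rationale: daily inpatient observation and phone contact differ in quality. The sponsor may have meant the second period as shorthand for everything after the completion or discharge visit, which would close the gap. The SAP does not say so, and that reading would leave the unequal time at risk untouched.

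Finally, SAP 4.13.2 specifies no hypothesis test for adverse events, and a misleading impression requires stays to differ and the first period to be read alone. This limits the consequence. It does not make the in-hospital percentages comparable.

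**Conclusion.** The point holds for the by-period report only. Its two periods do not cover follow-up, and its in-hospital comparison depends on a post-randomization outcome with no allowance for time at risk. Severity is minor to moderate.

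The 2.5 to 8 point gap illustrates direction and order of size. It rests on assumed hazards and stays, constant risk, exponential stay and no deaths, and it vanishes if time in hospital is equal between arms. It should not be read as a forecast that the drug arm will look safer: the direction follows whichever arm spends less time in hospital, for whatever reason. Nor should the 3.0% to 13.5% still in hospital after Day 28 be read as the share with an unassigned event. Those patients' events up to Day 28 are in the first period, and only later inpatient events are left out.

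**What to change.** In SAP 4.13.2:
1. Keep the unsplit tables as planned.
2. Define the by-period report by study day regardless of hospital status: Day 1-28, and Day 29 to the Day 60 contact, for all Safety Analysis Set patients.
3. State that post-baseline runs from first dose to the last adverse event contact.
4. If the hospital-status split is kept, label it supplementary, add a category for in hospital after Day 28, and report patient-days at risk with each period.

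The cost is SAP wording and re-cut tables. Event dates are already collected, and SAP 4.3.3 has rules for missing ones. The downside is that the fixed Day 1-28 window mixes daily inpatient observation with phone recall. A patient discharged on Day 9 is next contacted at about Day 28, some 19 days later. Under-reporting by phone would leave a smaller bias in the same direction, so the change reduces the problem rather than removing it.

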6.2. Exclusion Criteria

Patients will be excluded from study enrollment if they meet any of the following criteria at screening, until specified otherwise:

1. Have ARDS and/or require immediate intermittent mandatory ventilation (IMV).
2. In the opinion of the investigator, is moribund irrespective of the provision of treatments.
3. Any concurrent serious medical condition (e.g. patients with estimated glomerular filtration rate [eGFR] < 15 mL/min/1.73m² or on dialysis, preexisting lung disease requiring O₂ at rest, a body mass index [BMI] that precludes techniques such as proning) or concomitant medication that in the opinion of the investigator that would preclude participation in the study.
4. Have received treatment with a drug predominantly targeting Ang2 activity (e.g., tyrosine kinase inhibitors and/or antibody treatment) within the past month or 5 half-lives, whichever is longer.
5. Have a known sensitivity to mAbs or other therapeutic proteins, to agents of similar biologic composition as LY3127804, or to any products used in the formulation of LY3127804 (refer to the IB for LY3127804 for details) or are incompatible with the treatment of LY3127804.

6. Have a known history or show evidence of human immunodeficiency virus (HIV) and/or hepatitis A, B or C
7. Exclusion Criterion [7] has been deleted.
8. Have a significant bleeding disorder or active vasculitis or had a Grade ≥ 3 bleeding episode within 12 weeks prior to receiving treatment
9. Have experienced any arterial thromboembolic event, including myocardial infarction, unstable angina, cerebrovascular accident, or transient ischemic attack, within 6 months prior to receiving treatment
10. Have experienced any Grade 3 or 4 venous thromboembolic event that is considered by the investigator to be life-threatening or that is symptomatic and not adequately treated by anticoagulation therapy within 6 months prior to receiving treatment. Patients with chronic portal vein thrombosis who are asymptomatic and not considered to need anticoagulation therapy are eligible.
11. Have chronic congestive heart failure (New York Heart Association class ≥ 3) or uncontrolled cardiac dysrhythmia
12. Have a serious nonhealing: (a) wound, (b) peptic ulcer, or (c) bone fracture, within 28 days prior to receiving first dose of study drug

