7.7. Concomitant Therapy

All concomitant therapies that are part of routine care are allowed and can be used during the study. If indicated, anticoagulation therapies, including full-dose anticoagulation therapies, are allowed.

All concomitant therapies must be recorded in the eCRF.

Concomitant medications captured should include unapproved (“off-label”) medication, such as, for example, convalescent antibodies, remdesivir, chloroquine, hydroxychloroquine, and IL-6 antagonists.

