8.1. Discontinuation from Study Treatment

Possible reasons leading to permanent discontinuation of study drug:

- Patient Decision
 - the patient requests to discontinue study drug.
- Investigator Decision
 - The investigator may discontinue treatment after the first dose, if in the judgement of the investigator the benefit/risk assessment for LY3127804 does not support administration of a second dose.
- Grade 3 or higher infusion-related reaction per National Cancer Institute Common Terminology Criteria for Adverse Events (NCI-CTCAE) 5.0 (refer to Section 9.2.2)
- Grade 2 and greater bleeding events associated with study treatment.

Patients discontinuing from the study drug prematurely for any reason should complete adverse event and other follow-up procedures per Section 2 (Schedule of Activities), Section 9.2 (Adverse Events), and Section 9.4 (Safety) of this protocol.

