9.2.1. Serious Adverse Events

Study-specific clinical outcomes of progressive pulmonary failure in hospitalized patients with presumed or confirmed COVID-19 are exempt from all serious adverse event reporting unless the investigator deems the event to be related to the administration of study drug. Monitoring by the DMC will include continuous assessment of a potential imbalance in aggregate events between the treatment and control groups (please refer to Section 9.4.5).

The following events will be considered clinical outcomes and not reported as SAEs:

- Death related to progressive pulmonary failure and/or ARDS, that is, related to severe ARDS or a sequela of ARDS based on the interpretation of the investigator.
- Cardiovascular events: cardiac failure.
- Respiratory events: pneumonia, hemoptysis, decreased PaO₂/FiO₂, mechanical ventilation/ECMO, hypoxia, hypoxemia, ARDS, acute lung injury, or respiratory failure.
- Systemic inflammatory response syndrome related criteria: tachypnea, hypopnea, leukocytosis, leukopenia, hypothermia, hyperthermia, tachycardia, or bradycardia.
- Secondary infections

An SAE is any AE from this study that results in one of the following outcomes and is not classified as a clinical outcome of COVID-19 using the definitions shown in Section 9.2.:

- death that is not related to COVID-19 or a sequela of COVID-19 or death that is considered by the investigator to be related to study drug
- prolonged inpatient hospitalization or re-hospitalization life-threatening experience (that is, immediate risk of dying)
- persistent or significant disability/incapacity
- congenital anomaly/birth defect

- important medical events that may not be immediately life-threatening or result in death or hospitalization but may jeopardize the patient or may require intervention to prevent one of the other outcomes listed in the definition above.

The study site personnel must alert the sponsor, or its designee, of any SAE as soon as practically possible but no later than 24 hours.

Additionally, study site personnel must alert the sponsor, or its designee, of any SAE within 24 hours of Investigator awareness of the event via a sponsor-approved method. If alerts are issued via telephone, they are to be immediately followed with official notification on study-specific SAE forms. This 24-hour notification requirement refers to the initial SAE information and all follow-up SAE information.

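### No planned output counts patients with any bleeding, or with Grade 2 or greater bleeding, by arm, although the protocol lists such bleeding as a possible reason to stop study drug.

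*SAP*

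**What the plan says.** Protocol 8.1, under the lead-in "Possible reasons leading to permanent discontinuation of study drug", includes "Grade 2 and greater bleeding events associated with study treatment". The summary of amendment (c) in Appendix 5 records that this item was added on FDA feedback. The same amendment removed the exclusion for anticipated full-dose anticoagulation, and Protocol 7.7 now reads "If indicated, anticoagulation therapies, including full-dose anticoagulation therapies, are allowed". Among the exclusions in Protocol 6.2 is: "Have a significant bleeding disorder or active vasculitis or had a Grade ≥ 3 bleeding episode within 12 weeks prior to receiving treatment".

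SAP 4.13.2 gives the main adverse-event summary: "TEAEs will be summarized for each treatment group by SOC and PT, and by PT in order of decreasing frequency of preferred term". Serious, drug-related, drug-withdrawal and maximal-severity summaries are also by system organ class (SOC) and preferred term (PT). The counting rule is that "A patient with multiple AEs (different PTs) coded to the same SOC will be counted only once for that SOC", with a further count for each different PT in that class.

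None of the 43 tables, 29 listings and 5 figures in SAP section 5 is for bleeding, and neither is any DMC output in SAP 4.16. The SAP names no grouped term or standard query. The only adverse event of special interest in the protocol (9.2.4) is secondary infection.

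**The concern.** The protocol acts on a category, treatment-associated bleeding of Grade 2 or more at any site. The SAP reports by single term and by body-system class. A reader of the final tables who wants to know how many patients bled on each arm, or bled at the grade the protocol acts on, will not find the number and cannot rebuild it by adding rows. If the drug raises bleeding modestly at several sites, the tables will show a few rows differing by one or two patients each, which is easy to read as chance. Because anticoagulation is allowed at full dose, background bleeding may also be appreciable, and this makes a clean patient-level count more useful.

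**Working it through.** **1. Can the count be read from the planned tables?** The documents state no figure on this point, so the check is of structure.

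- *Tables 9, 10, 12 and 14* (all, related, serious and fatal TEAEs) are by SOC and PT. A patient with two bleeds under different PTs is in two PT rows, and in two SOC rows if the classes differ.
- *Table 11* (maximal severity) takes the maximum within a SOC or PT. Grade 2 or more can be read for one term, but not across bleeding terms.
- *Table 13* depends on this rule: "TEAEs for which the action taken with medication is ‘Drug Withdrawal’ will be identified as TEAEs that lead to study drug discontinuation". Dosing is on Days 1 and 15 only, and a patient discharged before Day 15 gets no second dose (Protocol synopsis). Once no dose remains, a bleed has no dosing to withdraw.
- *SAE outputs.* Protocol 9.2.1 lists, among clinical outcomes not reported as SAEs unless judged related to study drug, "Respiratory events: pneumonia, hemoptysis, decreased PaO₂/FiO₂, mechanical ventilation/ECMO". Some hemoptysis can therefore be missing from SAE tables, including the DMC's.
- *Table 8* (overview) has no bleeding row.

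**2. What the rows leave undetermined.** If k rows each hold m patients, the number of distinct patients lies between m (complete overlap) and k × m (no overlap). Take 5 rows, 1 patient each on placebo and 3 each on drug:

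- placebo: between 1 and 5 patients with any bleeding
- drug: between 3 and 15
- difference: between 3 − 5 = −2 and 15 − 1 = 14 patients

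The same displayed rows fit anything from no excess to a large one.

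**3. How much visibility is lost.** The documents give no bleeding rates, so the rates below are assumptions. Inputs: 100 per arm (SAP 3.2, evaluable patients) and a one-sided Fisher exact test at 0.05, used only as a yardstick. Events are split evenly over k = 5 or 6 terms. With per-row power r, the chance that at least one of k independent rows reaches 0.05 is 1 − (1 − r)^k, with no multiplicity adjustment.

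| Assumed any-bleeding rate, placebo v drug | Pooled count | One given row, k = 5 / 6 | At least one row, k = 5 / 6 |
|---|---|---|---|
| 5% v 15% | 71% | 7.9% / 5.1% | 34% / 27% |
| 4% v 12% | 58% | 4.6% / 2.7% | 21% / 15% |
| 5% v 10% | 28% | – | – |

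For example, 1 − (1 − 0.079)^5 = 0.34 and 1 − (1 − 0.051)^6 = 0.27.

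Single rows are weak because the counts are small. With none on placebo, 4 on drug gives p = (100·99·98·97)/(200·199·198·197) = 0.061. A fifth patient multiplies this by 96/196, giving 0.030. A row therefore needs at least 5 v 0, while the assumed 15% spread over 5 rows puts about 3 patients in each.

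**The case against.** A reader might infer that bleeding is never compared between arms. The documents do not support that. Each bleeding term appears by treatment group in Table 9, and where applicable in Tables 10 to 14. Hemoptysis recorded as an AE, and bleeds after the last dose, still enter Tables 9 and 11. What is missing is the pooled patient count.

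A reader might also infer that bleeding is the trial's designated safety concern, or that Protocol 8.1 makes discontinuation automatic. Neither is supported. The designated special-interest event is secondary infection, and Protocol 6.2 excludes many other conditions besides bleeding. The 8.1 list is of possible reasons and is limited to bleeding associated with study treatment. The support for singling bleeding out is narrower: it is a listed stopping reason, added on regulatory feedback.

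Nor can one say that the trial would report a bleeding excess as absent. Patient-level listings exist, the DMC sees unblinded TEAE and SAE tables and may run further safety analyses (Protocol 9.4.5), and exploratory analyses are permitted. These routes are real, but a grouping made after unblinding has a term list chosen with the results in view.

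The numerical contrast also needs care. SAP 4.13.2 plans no adverse-event test. Comparing the pooled count with one given row exaggerates the loss, because readers scan every row; the at-least-one-row figures are the fairer comparison. An even split is unfavourable: if one term carried 60% of events (3% v 9%), that row alone would reach 43%. A pooled table would also usually miss a doubling from 5% to 10%. All of this stands and limits the size of the point, not its existence.

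**Conclusion.** The gap is real and modest. No planned output gives, by arm, the number of patients with any bleeding or with Grade 2 or greater bleeding, and the counting rule prevents that number from being recovered from the tables. Under a threefold excess (5% v 15%), pooling raises the chance of a visible signal from about 27-34% to 71%; at 4% v 12%, from about 15-21% to 58%. These figures rest on assumed rates, an even split over 5 to 6 terms, independent rows, and a test used only to express visibility.

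The structural conclusion needs none of these. It needs only that bleeding at different sites is coded under more than one term, which is itself an assumption about the dictionary that the documents do not spell out. The supportable statement is that a spread-out excess could be overlooked, not that it would be.

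**What to change.** Add to SAP 4.13.2 and list 5.1 one descriptive table of treatment-emergent bleeding by treatment group:

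- a grouped term list fixed before unblinding, for example a MedDRA haemorrhage query;
- each patient counted once, with an any-grade row and a Grade 2 or greater row;
- hemoptysis recorded as an AE included, whatever its SAE status;
- the risk difference between arms with its confidence interval (SAP 4.1 already gives a 90% interval for differences in proportions);
- a split by recorded anticoagulant use at first dose, and by therapeutic intensity only if the concomitant-medication data capture it.

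Add the same table to the DMC outputs in SAP 4.16.

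The cost is SAP wording and one programmed table. Adverse events are already MedDRA-coded and CTCAE-graded, and concomitant therapies are already recorded. Whether anticoagulant dose or intensity is captured cannot be confirmed from the documents. The table needs no protocol change and leaves the clinical discontinuation rule as it is.
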